Ab=antibody; ADE=adverse device effect; AE=adverse event; BKZ=bimekizumab; BSA=body surface area; CT=computed axial tomography; DLQI=Dermatology Life Quality Index; ECG=electrocardiogram; eCRF=electronic Case Report Form; HBcAb=anti-hepatitis B core antibody; HBsAg=hepatitis B surface antigen; HBV=hepatitis B virus; HCV=hepatitis C virus; HIV=human immunodeficiency virus; IGA=Investigator's Global Assessment; IGRA=interferon-gamma release assay; IMP=investigational medicinal product; IRT=interactive response technology; P-SIM=Psoriasis Symptom and Impact Measure; PASI=Psoriasis Area and Severity Index; PEOT=Premature End of Treatment; PSD=Patient Symptom Diary; Q4W=every 4 weeks; Q8W=every 8 weeks; scalp IGA=scalp-specific IGA; SFU=Safety Follow-Up; TB=tuberculosis

Note: All assessments should be performed prior to IMP administration. The IMP administration is the starting point for the next administration period. Thus, the assessments in Week 16 and Week 32 belong to the previous treatment period.

^a For visits from the first dose of IMP through Week 32, the visit window is ± 4 days from the scheduled visit. For the SFU Visit, the visit window is ± 7 days from the scheduled visit.

^b The SFU Visit will occur 17 weeks after the final dose of IMP.

^c Ensure no significant changes in medical history.

^d Includes evaluation of signs and symptoms of active TB and risk for exposure to TB.

^e The physical examination will be performed as described in Section 8.2.3.

^f Vital signs (sitting systolic and diastolic blood pressure, pulse rate, and body temperature) are to be measured prior to blood sampling and prior to dosing, where applicable.

^g Pregnancy testing will consist of serum testing at Screening. A urine pregnancy test will be administered at all other visits.

^h Study participants who have evidence of or test positive for hepatitis B or C are excluded from the study, per Exclusion Criterion #9 (Section 5.2). A positive test for HBV is defined as: 1) positive for HBsAg or 2) positive for HBcAb. A positive test for HCV is defined as: 1) positive for anti-HCV Ab and 2) positive via a confirmatory test for HCV (eg, HCV polymerase chain reaction).

ⁱ The HIV test results will not be recorded in the eCRF.

^j Screening chest x-ray/CT scan must occur within 3 months prior to Screening Visit.

Table 1-1: Schedule of Activities

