Note: After a study participant completes the Week 16 assessments, which are the last assessments of the Initial Treatment Period, the dose of IMP for the Maintenance Treatment Period will be administered according to the randomization scheme. The final assessments of the Maintenance Treatment Period will be performed at Week 32. No IMP will be administered at Week 32.

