Derived variables in general will display the mean, SD and median to 1 more decimal place than the variables used in the derivation. If the number of decimal places reported in the raw data is varied then use either the maximum raw number of reported decimal places or 3, whichever is the lowest, as a guide for the descriptive statistics.

Statistical tests of efficacy variables will be presented as two-sided p-values rounded to three decimal places. P-values less than 0.001 will be presented as “<0.001” and p-values greater than 0.999 will be presented as “>0.999”. Statistical comparisons will be two-sided and will be performed at the 0.05 level of significance.

A complete set of data listings containing all documented data as well as calculated data (eg, change from Baseline) will be generated.

Unless otherwise stated, the IMP administration in the Maintenance Treatment Period includes both active IMP (bimekizumab) and placebo injections for study participants randomized to BKZ Q4W in the initial treatment period and switch to BKZ Q8W in the Maintenance Treatment Period.

Per protocol, for visits from the first dose of IMP through Week 32, the visit window is ± 4 days from the scheduled visit. For the SFU Visit, the visit window is ± 7 days from the scheduled visit. All by-visit summaries will contain nominal (ie, scheduled) visits only. Unscheduled visits will not be mapped to scheduled visits except for assessments that occur within a 4-day time window of a scheduled visit and the relevant scheduled visit data is not available. In that case, the assessment will be mapped to the corresponding scheduled visit and will be used for the analysis. If multiple unscheduled visits are remapped to one scheduled visit, the data collected on a day nearest to the scheduled visit day will be used in the analysis. This will only occur for some vendor data (questionnaire data such as PASI, IGA, PSD, scalp IGA, and DLQI data).

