4.1.3 Mapping of assessments performed at Early Discontinuation Visit

If the PEOT visit occurs at a scheduled visit as outlined in the schedule of assessments, then no mapping is necessary, and any PEOT assessments should correspond to that scheduled visit. PEOT visit assessments that occur on a date after a scheduled visit will be assigned to the next scheduled site visit per the protocol following the last visit where assessments were available regardless of the given assessment actually collected per the protocol SoA.

This approach means that there is a chance that data will be mapped to a visit where a given assessment was not actually collected per the protocol SoA. If that happens, those data will not be summarized in by-visit tables (though they will be available in the listings).

The only exception to the above rule is for anti-bimekizumab antibody assessments, in which all PEOT visit assessments will be assigned to the next scheduled visit at which anti-bimekizumab antibody are assessed.

All by-visit summaries will contain nominal visits only. Unscheduled visits will not be mapped to scheduled visits. However, in cases where vendor data (questionnaire data such as PASI, IGA, PSD, scalp IGA, and DLQI data) is assigned to an unscheduled visit instead of a scheduled visit, the assessments will be mapped into the scheduled visit if the assessments dates fall into the permissible window, as detailed in Section 4.1.

Note that based on the early withdrawal mapping conventions described above, a mapped PEOT visit is considered as observed at that visit and should be summarized as such in the tables.

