4.4.3 Time to PASI75/90/100 response

Time to PASI75/90/100 response (in days) during the ITP will each be calculated as:

Min (Date of first PASIxx response, Date of Week 16 visit) – Date of First Dose + 1

with xx representing 75, 90, 100 respectively. All visits up to and including Week 16 visit (including unscheduled visits) will be considered.

Study participants who discontinue IMP without achieving a given PASI response (either PASI75, PASI90, or PASI100 response, respectively) prior to Week 16 visit will be censored at the date of the last observed PASI assessment on or prior to IMP discontinuation. Study participants who reach the Week 16 visit without achieving the given PASI response will be censored at the date of the last observed PASI assessment on or prior to the Week 16 visit. Study participants who miss the Week 16 visit but start the MTP without achieving a give PASI response will be censored at the date of the last observed PASI assessment on or prior to the first IMP administration in MTP. Study participants will be censored at Baseline if there is no Baseline PASI assessment or no post-Baseline PASI assessment.

Time to PASI75/90/100 response during the ITP will each be estimated and presented using the Kaplan-Meier product-limit method for each treatment group.

Kaplan-Meier plots of time to PASI responses will also be presented by treatment group. In these Kaplan-Meier plots, the line will start at 0 (since there are no responders at Day 0) and will increase over time, representing time to achieving the response.

The median time to response, including the 2-sided 95% CI, will be calculated for each treatment group. Comparisons of bimekizumab versus placebo will be analyzed using a log-rank test.

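### When the scheduled Week 16 score is not available, the SAP's 4-day mapping rule can fill it with a PASI or IGA taken after the Week 16 dose

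*Protocol*

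**What the plan says.** **Intended order.** The note to the Schedule of Activities (Protocol 1.3) puts all assessments before dosing and concludes: "Thus, the assessments in Week 16 and Week 32 belong to the previous treatment period". Protocol 4.1 repeats this for Week 16. So does the note to Table 6-2 in Protocol 6.1, which opens "After a study participant completes the Week 16 assessments, which are the last assessments of the Initial Treatment Period" and only then has the maintenance dose given. Table 6-2 shows the placebo arm moving to bimekizumab at that dose. SAP 4.1.1.2 ends the Initial Treatment Period just before the first maintenance dose.

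**Mapping rule.** SAP 4.1 states: "Unscheduled visits will not be mapped to scheduled visits except for assessments that occur within a 4-day time window of a scheduled visit". A second condition limits this to cases where "the relevant scheduled visit data is not available". If several unscheduled values qualify, "the data collected on a day nearest to the scheduled visit day will be used in the analysis". On scope it says: "This will only occur for some vendor data (questionnaire data such as PASI, IGA, PSD, scalp IGA, and DLQI data". SAP 4.1.3 restates the rule for vendor data filed under an unscheduled visit: "the assessments will be mapped into the scheduled visit if the assessments dates fall into the permissible window". Neither section mentions the dose, and Week 16 is not excepted.

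**Dose timing elsewhere in the SAP.** For time to PASI response (SAP 4.4.3), a participant who misses Week 16 but starts maintenance without a response is censored at "the last observed PASI assessment on or prior to the first IMP administration in MTP". SAP 4.1.2 discusses Baseline values recorded after the first dose and accepts them only if taken on the dosing day.

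**The concern.** The Week 16 comparison is placebo-controlled only for scores taken before the Week 16 dose. A rule that looks only at calendar distance can carry a score across that boundary. The period definitions and the time-to-response analysis respect the boundary; the visit values behind the confirmatory endpoints do not.

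Without a mapped value, SAP 4.2.2 and 4.3.1.2 score the participant as a nonresponder. In those analyses, mapping can therefore only leave a nonresponder unchanged or create a responder. The endpoints reached are:

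- PASI90 and IGA 0/1 at Week 16 (co-primary);
- PASI100 at Week 16 (key secondary);
- the PSD itch, pain and scaling responses at Week 16 (additional secondary);
- PASI75 at Week 4 (key secondary, third in the test sequence), where the dose crossed is the second one.

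A mapped value also counts as available in the observed-case analysis of the key secondaries (SAP 4.3.1.3), so that analysis would not expose it. It can also decide who is a Week 16 responder in the maintenance summaries (SAP 4.4.1).

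**Working it through.** The plan gives no figure to reproduce here. The check has three parts.

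**1. How long after the dose can the value be?** Take the first dose as Day 1.

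- Planned Week 16 day = 1 + 16 × 7 = 113. A ±4-day window is Days 109 to 117.
- Window centred on the actual visit, with dosing at that visit: at most 4 days after the dose.
- Window centred on the planned day, dosed on Day 109 and assessed on Day 117: 117 − 109 = 8 days.
- Week 4: planned day 1 + 4 × 7 = 29, window Days 25 to 33, giving the same 4 or 8 days after the second dose.

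The text does not settle which centre applies. The main rule refers to the scheduled visit, the tie-break to the scheduled visit day.

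**2. What is one participant worth?** The planned arms are 90 and 30 (Protocol 4.1, SAP 1.2).

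- Placebo: 1/30 = 3.3 percentage points.
- Bimekizumab: 1/90 = 1.1 percentage points.

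The documents give no frequency of remapping. Assuming 0 to 3% of participants have remapped data, 0.03 × 30 = 0.9 and 0.03 × 90 = 2.7, so 0 to 1 placebo and 0 to 3 bimekizumab participants. This is an upper bound for the assumed range, because remapped values include correctly timed scores that were only mislabelled.

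**3. Could a test result change?** The readable text gives no response rates, so bimekizumab rates of 60% to 90% are assumed. With a and b responders in arms of 90 and 30, N = 120 and m = a + b, the unstratified CMH statistic is (a − 90m/N)² / [90 × 30 × m(N − m) / (N²(N − 1))]. At the least favourable assumed rate, 60% (a = 54):

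| Placebo responders of 30 | Risk difference (points) | CMH | Fisher p |
|---|---|---|---|
| 0 | 60.0 | 32.5 | 0.0000000006 |
| 1 | 56.7 | 28.9 | 0.000000009 |
| 2 | 53.3 | 25.5 | 0.0000001 |
| 3 | 50.0 | 22.4 | 0.000001 |
| 5 | 43.3 | 16.8 | 0.00004 |

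At 90%, moving from 0 to 2 placebo responders changes the risk difference from 90.0 to 83.3.

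For the opposite direction, remove 3 bimekizumab responders at the 60% rate with 2 placebo responders. Then a = 51, m = 53, and the statistic is (51 − 39.75)² / 5.595 = 22.6, against 25.5 with a = 54. The bimekizumab rate falls from 60.0% to 56.7%. Both values are far above 3.84, the two-sided 5% limit. This covers Week 4 only if the PASI75 rate lies in the assumed range.

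**The case against.** The best defence is that the rule exists to correct visit labels. SAP 4.1.3 describes vendor data assigned to an unscheduled visit when it belonged to a scheduled one, and the natural case is a pre-dose Week 16 score filed under the wrong label. To be affected, a participant must be dosed at Week 16 with no available scheduled score, contrary to the protocol's order. The participant must then be assessed after the dose but inside the window, and must meet the response criterion on that score. The 8-day figure also needs the earliest dosing day and the latest assessment day. All of this stands and makes the case rare.

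A reader might infer that placebo responses are routinely read after the switch, or that the rule threatens the co-primary conclusions. The documents do not support either. Mapping applies only when the scheduled value is not available. A placebo participant turned into a responder works against bimekizumab, and a 90% improvement from a PASI of at least 12 within 4 to 8 days of a first active dose is unlikely. The direction is not uniformly conservative, though: mapping also rescues bimekizumab participants from imputed nonresponse, after a further active dose at Week 4 or Week 16.

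Nor can one infer that no safeguard exists anywhere. SAP 6.8.1.1 appears in the contents, and the version history says a definition of missing efficacy data was clarified there, but its text is not in this copy. The end of the Initial Treatment Period in SAP 4.1.1.2 might also lead a programmer to drop a post-dose value. That leaves the matter to interpretation: the mapping rule does not refer to that boundary, and a value already mapped may no longer count as missing.

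**Conclusion.** The gap is real but minor. As SAP 4.1 and 4.1.3 read, a score dated up to 4 days after the Week 16 dose, or up to 8 on the planned-day reading, can become the Week 16 value when the scheduled one is not available. This conflicts with the order in Protocol 1.3, 4.1 and 6.1 and with the period boundary in SAP 4.1.1.2, and it is inconsistent with the cut in SAP 4.4.3. The protocol text is sound; the omission is in the SAP.

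The effect is on the definition of the endpoints and, slightly, on the estimates. No change of significance is expected. That rests on the assumed remapping frequency of 0 to 3% and assumed bimekizumab response rates of 60% to 90%. The conclusion about the text is subject to whatever SAP 6.8.1.1 contains. This is a low-priority clarification, worth making because it removes a possible bias at almost no cost.

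**What to change.** Add one condition to SAP 4.1 and repeat it in SAP 4.1.3: an unscheduled assessment is mapped to a dosing visit only if its date is on or before the date of that visit's IMP administration; for Week 16, the reference is the first IMP administration in the Maintenance Treatment Period. Same-day values are accepted, as SAP 4.1.2 does for Baseline. Otherwise the visit value stays missing and NRI applies. State in the same place whether the 4 days are counted from the planned day or from the actual visit, and check that SAP 6.8.1.1 agrees.

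A date-level condition is enough. Requiring the clock time to precede the dose would discard same-day scores with a late time stamp, be stricter than the Baseline convention, and turn some genuine Week 16 scores into nonresponse.

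The cost is one sentence in each section and one date comparison in the mapping program. The downside is that a few post-dose values become missing and are scored as nonresponse.

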6.1.1 Medical devices

The UCB-manufactured medical device provided for use in this study is the 1mL PFS.

Instructions for medical device use are provided in the IMP Handling Manual.

All adverse device effects (ADEs) and device deficiency (including malfunction use error and inadequate labeling) shall be documented and reported by the Investigator throughout the study (see Section 8.3.9) and appropriately managed by the Sponsor.

6.2 Preparation, handling, storage, and accountability requirements

Unblinded study staff will be responsible for preparation of the clinical study material, including recording the administration information on source documents and administration of the IMP as sc injections. The unblinded personnel will not be involved in the study in any way other than assuring the medication is taken from the correct kit and administering the IMP to the study participants.

Only study participants enrolled in the study may receive IMP, and only authorized site staff may supply or administer IMP. All IMP must be stored in a secure, environmentally controlled, and monitored (manual or automated) area in accordance with the labeled storage conditions, with access limited to the Investigator and authorized site staff.

The Investigator, institution, or the head of the medical institution (where applicable) is responsible for IMP accountability, reconciliation, and record maintenance (ie, receipt, reconciliation, and final disposition records).

The Investigator or designee must confirm appropriate temperature conditions have been maintained during transit for all IMP received and any discrepancies are reported and resolved before use of the IMP.

In case an out-of-range temperature is noted, it must be immediately reported as per instructions contained in the IMP Handling Manual.

Further guidance and information for the final disposition of unused IMP are provided in the IMP Handling Manual.

6.2.1 Drug accountability

During the Initial Treatment Period and Maintenance Treatment Period of this study, the IMP will be administered in the clinic, and compliance will be determined at the visit by study personnel.

The Drug Accountability Form will be used to record IMP dispensing and return information on a by-participant basis and will serve as source documentation during the course of the study. Details of any IMP lost, damaged (due to breakage or wastage), not used, partially used, disposed of at the study site, or returned to the Sponsor or designee must also be recorded on the appropriate forms. All supplies and pharmacy documentation must be made available throughout the study for UCB (or designee) to review.

In order to maintain the blind, all IMP documentation (eg, shipping receipts, drug accountability logs, interactive response technology [IRT] randomization materials) must be maintained and accessed by unblinded, trained site personnel only. Designated, unblinded site personnel must be appropriately trained and licensed (per country guidelines) to administer injections.

Unblinded study staff will be delegated the responsibility to receive, inventory, and destroy the used kits. The packaging identifies each kit by a unique number, but due to the open-label packaging, the unblinded study staff will be responsible in order to maintain the blind. Unblinded study staff will be responsible for preparation (breaking tamper proof sticker on kit, etc) of the clinical study material, including recording the administration information on source documents.

The Investigator (or designee) is responsible for retaining all used, unused, and partially used containers of IMP until returned or destroyed.

The Investigator may assign some of the Investigator's duties for IMP accountability at the study site to an appropriate pharmacist/designee.

The Investigator must ensure that the IMP is used only in accordance with the protocol.

Periodically, and/or after completion of the clinical phase of the study, all used (including empty containers)/partially used, unused, damaged, and/or expired IMP must be reconciled and either destroyed at the site according to local laws, regulations, and UCB standard operating procedures, or returned to UCB (or designee). Investigational medicinal product intended for the study cannot be used for any other purpose than that described in this protocol.

6.3 Measures to minimize bias: randomization and blinding

An IRT will be used for assigning eligible study participants to a treatment regimen (as applicable) based on a predetermined production randomization and/or packaging schedule provided by UCB (or designee). The randomization schedule will be produced by the IRT vendor. The IRT will generate individual assignments for kits of IMP, as appropriate, according to the visit schedule.

At the Screening Visit, each study participant will be assigned a 5-digit number that serves as the study participant identifier throughout the study. The study participant number will be required in all communication between the Investigator or designee and the IRT regarding a particular study participant. Once a study participant number has been assigned, it must not be reassigned.

At the Baseline Visit, a study participant will be randomized into the study. The Investigator or designee will use the IRT for randomization. The IRT will automatically inform the Investigator or designee of the study participant's randomization number. The IRT will allocate kit numbers to the study participant based on the randomization number during the course of the study.

Study participant numbers, randomization numbers, and kit numbers will be tracked via the IRT.

6.3.1 Procedures for maintaining and breaking the treatment blind

6.3.1.1 Maintenance of study treatment blind

All study participant treatment details (bimekizumab or placebo) will be allocated and maintained by the IRT system.

In order to maintain the blind, all IMP documentation (eg, shipping receipts, drug accountability logs, IRT randomization materials) must be maintained and accessed by unblinded, trained site personnel only. Designated, unblinded site personnel must be appropriately trained and licensed (per China guidelines) to administer injections.

Unblinded study staff will be delegated the responsibility to receive, inventory, and destroy the used IMP. The packaging identifies each kit by a unique number. Unblinded study staff will be responsible for preparation (breaking tamper proof sticker on kit, etc) of the IMP, including recording the administration information on source documents. To protect the blinding of the dosing regimen during the Maintenance Treatment Period, study participants receiving bimekizumab 320mg Q8W will also receive placebo injections at visits in between dosing so that all participants receive injections Q4W.

6.3.1.2 Breaking the treatment blind in an emergency situation

The integrity of this clinical study must be maintained by observing the treatment blind. In the event of an emergency for which the appropriate treatment for a study participant cannot be made without knowing the treatment assignment, it will be possible to determine to which treatment arm and dose the study participant has been allocated by contacting the IRT. All sites will be provided with details of how to contact the system for code breaking at the start of the study. The Medical Monitor should be consulted prior to unblinding.

The Clinical Project Manager (CPM) will be informed immediately via the IRT when a code is broken but will remain blinded to specific treatment information. Any unblinding of the IMP performed by the Investigator must be recorded in the source documents and on the Study Termination eCRF page.

